## 6. Safety evaluation

6.1 Adverse events: Any adverse medical events occurring during the study period are defined as adverse events, such as drug reactions, adverse reactions associated with ovarian stimulation, complications associated with pregnancy, and other discomfort complaints

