**Plan of follow-ups:**

	Screening and randomization	IVF/ICSI treatment		Follow-up		
	V1	V2	V3	V4	V5	V6
	Before IVF/ICSI treatment	IVF/ICSI treatment cycle	Thawed ET cycle	2 weeks after ET	4-5 weeks after ET	12 weeks of gestation
Informed consent	√					
Eligibility Criteria	√					
Personal information	√					
History	√					
Companied medication	√	√	√	√	√	√
Physical examination	√					
Vital signs	√	√	√			
Sex hormones	√	√	√			
Ultrasound	√	√	√		√	√
Complication and adverse events		√	√	√	√	√

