### 4. Research design

This study is a prospective, randomized, controlled and superiority clinical trial. Subjects will be recruited from the infertile patients undergoing IVF/ICSI at the Reproductive Medicine Center of Sun Yat-sen Memorial Hospital, Sun Yat-sen University.

The treatment group begins to take Reco-18 on the 1st to 5th day of menstruation with a dosage of 4 pills per day for the whole menstrual cycle, then perform ovulation induction on the second menstrual cycle, and continue to take Reco-18 until the day of oocyte retrieval. The control group

takes the multi-vitamins (Elevit, Bayer S.A.) with the dosage of one tablet per day as the same period in the treatment group.

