c. Oocyte retrieval, luteal support and embryo transfer: oocyte recovery is performed 34 to 38 hour after the trigger. Luteal support is provided on the day of oocyte retrieval, with vaginal micronized progesterone capsules (600mg/day) combined with oral dydrogesterone (30mg/day) until the pregnancy test. With the use of conventional IVF or ICSI fertilization, 1 to 2 cleavage stage embryos or day 5 blastocysts are transferred to the uterus, and the rest available embryos are cryopreserved.

d. If fresh embryo transfer is cancelled due to medical reasons, pregnancy outcome of the first thawed embryo transfer is collected. The endometrial preparation, thawed embryo transfer and luteal support are based on the routine operation.

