#### 6.2 Adverse events report:

Mild adverse events are recorded in the progress note.

Serious adverse events are submitted to Medicine Ethics Committee within 48 hours of occurrence.

6.3 Safety indexes are adverse events occurring in the treatment group and the control group, such as gastrointestinal reactions and allergies.

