#### 7.3 Safety indicators

Use descriptive statistics to summarize laboratory examination and vital signs as safety evaluation indicators, and summarize the changes of each index relative to the baseline. The indexes are classified as normal or abnormal (without clinical significance), and calculated the case number and percentage in each classification. Other safety indicators are summarized or listed as appropriate.

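### The safety comparison covers the whole study period with no on-product window, so gastrointestinal complaints arising after both products stop can dilute or shift it (minor; cheap improvement)

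*Combined protocol and SAP*

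**What the plan says.** **Adverse event definition.** Section 6.1: "Any adverse medical events occurring during the study period are defined as adverse events". Its examples include drug reactions, reactions to stimulation, pregnancy complications and other complaints.

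**Safety indexes.** Section 6.3: "Safety indexes are adverse events occurring in the treatment group and the control group, such as gastrointestinal reactions and allergies". No time limit is attached.

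**Exposure.** Section 4: "The treatment group begins to take Reco-18 on the 1st to 5th day of menstruation", and women in that arm "continue to take Reco-18 until the day of oocyte retrieval". The control product is taken "with the dosage of one tablet per day as the same period in the treatment group". Both arms therefore come off product at retrieval.

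**What starts then.** Section 5.8.5 c: "Luteal support is provided on the day of oocyte retrieval". It consists of vaginal progesterone and oral dydrogesterone. Transfer follows, either fresh or, if the fresh transfer is cancelled, in a thawed cycle.

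**Collection.** In the follow-up schedule, the row "Complication and adverse events" is ticked from V2 (the IVF/ICSI cycle) to V6 (12 weeks of gestation). Section 5.8.7 ends follow-up after a negative pregnancy test.

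**Analysis.** Section 7.1 defines who is in the Safety Set, not which dates count. Section 7.3 is descriptive and ends: "Other safety indicators are summarized or listed as appropriate". Section 7.4.4 has the team judge, before database lock, how adverse events are associated with the study.

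**The concern.** Gastrointestinal reactions and allergies are the only safety indexes that section 6.3 names. A gastrointestinal reaction to a four-pill daily regimen would be expected while the woman is taking it. The plan counts that reaction in the same period as nausea under luteal support or in early pregnancy, weeks after the last dose.

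Two things follow. A real difference between the products becomes harder to see. And because off-product nausea is partly a consequence of pregnancy, an arm with more pregnancies can look less tolerable when the product has no such effect. That second risk matters here because the trial is designed to show a higher pregnancy rate in the RECO-18 arm.

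**Working it through.** The documents state no adverse event rate and no safety power, so there is no figure of the plan's own to reproduce. The inputs from the documents are 40 women per arm (section 5.1) and a 0.05 significance level (section 7), taken as two-sided. All event rates, pregnancy rates and durations below are assumptions.

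**1. Share of observed time off product**

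Assume a 28-day cycle, the antagonist protocol and 9 to 12 days of stimulation, with retrieval two days after the last stimulation day.

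- Shortest course: start on day 5 (24 days in the first cycle), stimulation from day 2 for 9 days, retrieval on day 12. 24 + 12 = 36 days.
- Longest course: start on day 1 (28 days), stimulation from day 4 for 12 days, retrieval on day 17. 28 + 17 = 45 days.
- Fresh transfer, ongoing pregnancy: with retrieval counted as 2 weeks of gestation, 12 weeks is 84 - 14 = 70 days later. Share off product: 70/(45 + 70) = 61% to 70/(36 + 70) = 66%.
- Fresh transfer on day 3 to 5, negative test 14 days later: 17 to 19 days. Share: 17/(45 + 17) = 27% to 19/(36 + 19) = 35%.
- An assumed 60-day course (for example, the long protocol), fresh transfer: 70/130 = 54% with ongoing pregnancy; 17/77 = 22% to 19/79 = 24% after a negative test.
- Thawed cycle starting 28 days after retrieval, ongoing pregnancy: 28 + 84 = 112 days. Share: 112/157 = 71% to 112/148 = 76%.

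**2. Dilution**

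Let p be the on-product gastrointestinal risk and b an independent off-product risk of the same kind of event, equal in both arms. The whole-period risk is 1 - (1 - p)(1 - b), so the risk difference becomes (1 - b) times the on-product difference.

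Power is by exact binomial enumeration with 40 per arm and the uncorrected Pearson test:

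| Off-product b | 5% v 25% becomes | Difference (points) | Power | Power for 10% v 30% |
|---|---|---|---|---|
| 0% | 5.0% v 25.0% | 20.0 | 76% | 63% |
| 2% | 6.9% v 26.5% | 19.6 | 69% | 59% |
| 5% | 9.8% v 28.8% | 19.0 | 60% | 52% |
| 10% | 14.5% v 32.5% | 18.0 | 48% | 43% |
| 20% | 24.0% v 40.0% | 16.0 | 33% | 32% |
| 30% | 33.5% v 47.5% | 14.0 | 26% | 26% |
| 50% | 52.5% v 62.5% | 10.0 | 16% | 15% |

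The loss runs from small to large over this range, and nothing in the documents says where in it the trial lies.

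**3. Shift when pregnancy rates differ**

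Suppose the product has no gastrointestinal effect (10% on product in each arm) and only pregnant women have off-product nausea. Whole-period risk = 1 - 0.9 x (1 - pregnancy rate x nausea rate).

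- Pregnancy 35% v 50%, nausea in 50%: 25.8% v 32.5%, a spurious excess of 6.8 points.
- The same with nausea in 70%: 32.1% v 41.5%, 9.5 points.
- These reach p < 0.05 in about 10% and 14% of trials, against about 5% by chance.
- Pregnancy 35% v 40%: 2.3 to 3.2 points, with p < 0.05 in about 6% of trials.

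**The case against.** The strongest reply is that section 6.3 does not pool everything. It names gastrointestinal reactions and allergies as kinds of event, and section 6.1 lists stimulation and pregnancy complications separately. This stands in part: an unlike event, such as a pregnancy complication, does not enter a gastrointestinal count. Nausea after retrieval does, because no date rule keeps it out.

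Section 7.4.4 plans an attribution step. It asks about association with the study rather than the product, gives no criteria, and does not restrict the safety indexes to related events. Section 7.1 mentions unblinding, but no masking procedure is described, and four pills a day are compared with one tablet. Case-by-case attribution could therefore differ by arm.

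The visit schedule gives rough timing, since V3 to V6 all follow retrieval. That helps, but V2 spans both the end of product use and early luteal support. The case report form is not among the documents, so whether it already holds onset dates is unknown.

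Recording events to 12 weeks of gestation is sensible for a product taken before conception, and randomised arms share much of the background. Both are true. The gap is the missing on-product summary, not the long follow-up. Power is also only a yardstick: section 7.3 is descriptive, and only the general chi-squared sentence in section 7 suggests a test.

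A reader might infer that off-product events swamp the gastrointestinal and allergy comparison. The documents do not support that. They give no event rates, off-product time is the minority after a fresh transfer with a negative test, and no mechanism links luteal support or pregnancy to allergy counts.

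**Conclusion.** The point holds in a limited form. Followed as written, the plan yields a whole-period gastrointestinal comparison that is diluted by the factor (1 - b) and open to a shift if pregnancy rates differ. For an assumed 5% v 25%, power falls from 76% to 69% at a 2% background and to 16% at 50%. The possible spurious excess is a few points and would seldom reach significance. These figures assume independent on- and off-product events and, for the power figures, a background equal in both arms. Allergy should not be counted among the affected comparisons.

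The severity is minor: 80 women, a study that the protocol calls a pilot, and descriptive safety reporting. It is still worth correcting, as a cheap improvement, because an undivided table can mislead with or without a p-value.

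**What to change.** In sections 6.3 and 7.3, keep the whole-period summary and add beside it:

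- An on-product summary of gastrointestinal and allergic events with onset from first dose to the day of oocyte retrieval, plus one fixed tail that is the same in both arms and stated in advance. Report it by arm with the risk difference and 95% confidence interval.
- A second table of events with later onset, with pregnancy complications expressed per clinical pregnancy.
- An onset date for every event on the case report form, including mild events, which section 6.2 sends only to the progress note.

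The cost is SAP wording and, if it is not already there, one case report form field; no patients or visits are added. The downside is fewer events in the on-product table, and a late reaction to the product would appear only in the second table.

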#### 6.2 Adverse events report:

Mild adverse events are recorded in the progress note.

Serious adverse events are submitted to Medicine Ethics Committee within 48 hours of occurrence.

6.3 Safety indexes are adverse events occurring in the treatment group and the control group, such as gastrointestinal reactions and allergies.

## 7. Data collection and management

The data are collected and managed by the study team members, and personal information involving subject privacy will not appear in the results except for necessary. It should be applied to view subject information in accordance with the rules and regulations of department. The information is only open to the team members, and strictly forbidden to share with irrelevant personnel.

Data are analyzed using SPSS 19.0 statistical software. Measurement data are expressed as mean  $\pm$  standard deviation, and categorical variables are described as percentages. Data are compared using the independent sample t-test or chi-squared test.  $P < 0.05$  is considered statistical significance.

#### 7.1 Data Analysis Set:

Full Analysis Set (FAS): the FAS include all randomized subjects receiving treatment at least once. According to the intent-to-treat population (ITT) principle, all randomized cases accepting intervention at least once should be analyzed.

Safety Set (SS): all randomized subjects accepting intervention at least once and receiving post-treatment safety evaluation at least once should be included in the SS. SS is the safety evaluation population for this trial.

Per-protocol population set (PPS): all subjects in the FAS without major protocol violation will be included. Major protocol violation should be defined in the statistical analysis plan before database locking and study unblinding. Subjects will be analyzed based on the treatment.

#### 7.2 Analysis of primary indicator and secondary indicators:

Analysis of primary indicator: the two-sample rate test is used to compare the ongoing pregnancy rate at 12 weeks' gestation in the treatment group and the control group. Categorical variable is compared between groups using Pearson chi-squared test or Fisher's exact probabilistic method. Based on the FAS, the primary endpoint calculates the ongoing pregnancy rate at 12 weeks' gestation and its 95% confidence interval. Logistic regression is used to analyze the baseline effects, and the adjusted factors included age, infertility length, BMI, AMH, AFC, ovulation stimulation protocol, etc.

Analysis of secondary indicators: measurement data are compared using independent sample test or nonparametric analysis, and categorical variables are compared using Pearson chi-squared test or Fisher's exact probabilistic method between groups. Measurement data are analyzed by covariance analysis, and qualitative indicators are analyzed by Logistic regression to evaluate the baseline effects. Adjusted factors refer to the analysis of primary indicators.

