#### 5.8 Research method

5.8.1 Collection of basal data: age, infertility length, weight, and body mass index (BMI).

5.8.2 Collection of basal endocrine indexes: follicle stimulating hormone (FSH), luteinizing hormone (LH), estradiol, testosterone, dehydroepiandrosterone sulfate (DHEAS), sex hormone binding globulin (SHBG), and anti-müllerian hormone (AMH).

5.8.3 Collection of biochemical indexes: alanine aminotransferase (ALT), aspartate aminotransferase (AST), creatinine, total cholesterol (TC), triglycerides (TG), high-density lipoprotein (HDL), low-density lipoprotein (LDL), apolipoproteins B (ApoB), high-sensitivity C-reactive protein (Hs-CRP), fasting glucose, and fasting insulin.

5.8.4 Ultrasound examination: bilateral ovarian size, follicle number, and antral follicle count (AFC);

5.8.5 Controlled ovarian stimulation and IVF/ICSI:

a. Controlled ovarian stimulation

Gonadotropin-releasing hormone (GnRH) antagonist protocol: gonadotropin (Gn) 100 IU to 250 IU/day is individually administered to stimulate follicular growth on the 2nd to 4th day of menstruation. GnRH antagonist is added when dominant follicle reaches  $\geq 14$ mm in diameter and LH level is  $\geq 10$ IU/L, and is stopped until the day of human chorionic gonadotropin (HCG) administration.

GnRH agonist long protocol: in the midluteal phase of the menstrual cycle confirmed by ultrasound or hormone test or after 2 weeks of oral contraceptive use, pituitary downregulation is achieved by injection of 0.93-1.87mg long-acting GnRH agonist. 14 to 21 days later, vaginal ultrasound and blood hormone tests are performed to evaluate the complete downregulation of the

pituitary gland. Ovarian stimulation is initiated with Gn 100U-250U/day, and adjustment of Gn dosage is performed according to serum hormone level and follicle growth.

b. Trigger: recombinant HCG of 250ug is administered to induce oocyte maturation when at least two follicle  $\geq 18$ mm or three follicles  $\geq 17$ mm or four follicles  $\geq 16$ mm in diameter.

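### Section 7.2 adjusts for stimulation protocol as a baseline factor, but it is treatment given after randomization and nothing requires the choice to be recorded before the envelope is opened

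*Combined protocol and SAP*

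**What the plan says.** For the primary endpoint, section 7.2 first names an unadjusted comparison: "the two-sample rate test is used to compare the ongoing pregnancy rate". It then adds a model: "Logistic regression is used to analyze the baseline effects", where "the adjusted factors included age, infertility length, BMI, AMH, AFC, ovulation stimulation protocol, etc". Secondary outcomes get unadjusted tests, followed by covariance analysis or logistic regression with the same covariates: "Adjusted factors refer to the analysis of primary indicators". The opening of section 7 attaches the 0.05 threshold to simple tests: "Data are compared using the independent sample t-test or chi-squared test".

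Section 5.8.5 describes two stimulation options. In the antagonist protocol, gonadotropin "is individually administered to stimulate follicular growth on the 2nd to 4th day of menstruation". In the long agonist protocol, down-regulation is given "in the midluteal phase of the menstrual cycle confirmed by ultrasound or hormone test or after 2 weeks of oral contraceptive use", and stimulation follows 14 to 21 days later. The section gives no rule for choosing between the two and no time by which the choice must be made.

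The follow-up table puts randomization at V1, before the IVF/ICSI cycle at V2. Section 5.5 has the investigator allocate from a sealed envelope and mentions no stratification. Section 4 starts the study product on day 1–5 of one menstrual cycle and places ovulation induction in the next.

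**The concern.** Adjusting for a baseline covariate is safe because randomization makes it independent of arm. That guarantee fails for a variable that can be settled after allocation. If the choice of stimulation protocol responds both to the arm and to something prognostic that is not in the model, conditioning on it links arm to that unrecorded prognosis. The adjusted treatment effect is then biased even when the product does nothing.

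The route is open here. No blinding procedure is described, and the regimens look different (four pills a day against one tablet). Section 7.1 refers to unblinding but sets up no blind. The results at stake are the adjusted model for ongoing pregnancy and, through the cross-reference, every adjusted secondary result. The open end of the covariate list also leaves room for other post-allocation variables.

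**Working it through.** **1. Is the protocol a baseline value?** Section 5.8.1 lists age, BMI and duration of infertility as basal data, and 5.8.2 lists AMH as a basal endocrine index. AFC is in 5.8.4 under ultrasound without a basal label, and the follow-up table schedules ultrasound at V1 and again at V2, V3, V5 and V6. Stimulation protocol is in none of 5.8.1–5.8.4; it appears only in 5.8.5, as treatment.

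**2. When is it delivered?** The documents give no cycle length. Assume 28 days (range 24–35), with mid-luteal taken as 7 days before the next period. The first product dose is on day 1–5.

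- Long protocol, mid-luteal day 28 − 7 = 21: 21 − 5 = 16 to 21 − 1 = 20 days after the first dose. Range: 17 − 5 = 12 (24-day cycle) to 28 − 1 = 27 (35-day cycle).
- Antagonist protocol, day 2–4 of the second cycle, which is day 30–32 counted from the start of the first: 30 − 5 = 25 to 32 − 1 = 31 days. Range: 26 − 5 = 21 to 39 − 1 = 38.

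Both therefore fall after allocation, so the choice can still be made or changed then. It may also be made earlier, for example when an oral contraceptive is used first. The documents do not say.

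**3. How large could the bias be?** The plan states no rates or effects, so every input below is assumed. The simulation uses n = 80 and a control rate of about 42%.

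- Outcome log odds ratios per SD: age −0.4, infertility duration −0.1, BMI −0.1, AMH 0.2, AFC 0.2, plus an unrecorded factor U.
- Protocol choice: logit = 0.5 × AFC + c × U ± a, with +a in one arm and −a in the other. At a = 0.45 about 60% against 40% receive a given protocol, a gap of about 20 points. At a = 0.9 it is about 65–70% against 30–35%, a gap of about 30–40 points.
- Shift = treatment log odds ratio with the protocol term minus that without it, from 600,000 subjects and no true effect.
- False benefit and false harm are each nominally 2.5% (10,000 trials per setting, Monte Carlo SE about 0.2 points). Power is at an odds ratio of 2.5 (SE about 0.5 points), without the protocol term → with it.

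| Setting | a | Shift | False benefit / harm, % | Power, % |
|---|---|---|---|---|
| Choice unrelated to arm | 0 | 0.00 | 2.6 / 3.1 | – |
| Arm only (c = 0) | 0.45 | none | – | 40.6 → 38.9 |
| Arm only (c = 0) | 0.9 | none | – | 41.4 → 35.8 |
| Weak U (c = 0.5, outcome 0.4) | 0.45 | −0.036 | 2.3 / 3.4 | 47.1 → 42.5 |
| Weak U | 0.9 | −0.070 | 1.7 / 3.9 | 46.9 → 35.8 |
| Strong U (c = 0.8, outcome 0.8) | 0.45 | −0.093 | 1.8 / 4.4 | 41.2 → 33.0 |
| Strong U (c = 0.8) | 0.9 | −0.183 | 1.2 / 5.9 | 41.3 → 25.1 |
| Strong U (c = 1.5) | 0.9 | −0.240 | 1.0 / 7.0 | 40.9 → 23.3 |

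Reversing the sign of the arm dependence mirrors the shifts: +0.037 and +0.069 for weak U; +0.097, +0.189 and +0.239 for strong U. In the strong settings false benefit then rises to 4.3–7.5%. The standard error in the strong settings is 0.52–0.56, so the largest shift is 0.24 / 0.56 ≈ 0.43 of a standard error. On the odds-ratio scale that is exp(−0.24) ≈ 0.79 or exp(0.24) ≈ 1.27.

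**4. Does recording the choice first remove the bias?** With the intended protocol drawn from the same logit without the arm term, the shift is 0.00, false benefit is 2.4–3.1%, false harm is 2.6–3.1%, and power is within about 2 points of the five-factor model.

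**The case against.** The strongest reply is about reach. The primary endpoint is tested first by an unadjusted comparison of rates, secondary outcomes also have unadjusted tests, and the 0.05 threshold is attached to simple tests. All of that stands, and none of it is touched by this point.

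Bias is also possible rather than shown. It needs dependence on arm and on unrecorded prognosis together, and the documents indicate neither. The person who opens the envelope is not said to be the one who chooses the protocol. History, hormones and ultrasound are all scheduled at V1, so the choice may in practice be made at screening. AMH and AFC, two likely drivers of the choice, are already in the model.

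The larger figures rest on strong inputs: between-arm gaps in protocol choice of about 20–40 points, and an unrecorded factor with twice the assumed outcome effect of age (0.8 against 0.4 per SD). Even the weak settings use those gaps. There the two error rates sum to 2.3 + 3.4 = 5.7% and 1.7 + 3.9 = 5.6%, essentially the no-bias total of 2.6 + 3.1 = 5.7%. The effect is a mild asymmetry with some loss of power under one sign.

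A reader might infer that the protocol is in fact chosen after allocation by someone who knows the arm, so that the adjusted results, or even the main result, are invalid. The documents do not support that. They are silent on when the choice is made, and the main test does not use the variable. What survives the objection is that a variable labelled baseline is not tied to baseline, and that tying it costs almost nothing.

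**Conclusion.** The point holds as a gap in the specification of the adjusted models. Stimulation protocol is treatment delivered after V1 and is adjusted for as a baseline effect, with nothing fixing the choice before allocation. Any bias is conditional and of unknown direction: absent if the choice is unrelated to arm, small with weak unrecorded prognosis, and material only when strong arm dependence and a strong unrecorded factor coincide. Impact is low to moderate and limited to the adjusted analyses.

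The sizes apply to a binary endpoint under assumed effects and an assumed control rate. Covariance analyses such as that of oocyte number were not quantified. The open end of the list is missing detail rather than a demonstrated bias; it matters here because it does not keep other post-allocation variables out. Confidence is medium, because the case report form is not among the documents and might already record the intended protocol.

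**What to change.** In section 7.2:

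- Drop stimulation protocol from the adjusted models, or replace it with the intended protocol, entered on the case report form before the envelope is opened and analysed as recorded whatever is later given.
- State that all covariates (age, BMI, duration of infertility, AFC, AMH) are the values measured at V1 before allocation. This matters most for AFC, because ultrasound is repeated at later visits.
- Delete the closing "etc." so that no post-allocation factor can enter.

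The secondary analyses inherit the change through the existing cross-reference. The cost is wording, at most one pre-allocation field on the case report form, and the freedom to add covariates later. No gain in power over the five-factor model is claimed. No view is taken on which stimulation protocol is used.

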**Statistical analysis:**

Data are analyzed using SPSS 19.0 statistical software. Measurement data are expressed as mean ± standard deviation, and categorical variables are described as percentages. Data are compared using the independent sample t-test or chi-squared test. P<0.05 is considered statistical significance.

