## **5. Research protocol**

### 5.1 Sample size

At first it is designed to include 80 infertile patients (40 cases in each group), then the sample size is calculated based on the preliminary study results.

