### 5.5 The measurement of research results

Primary indicator: the ongoing pregnancy rate at 12 weeks' gestation.

Secondary indicators: the number of oocytes retrieved, the normal fertilization rate and the rate of high quality embryos, implantation rate, clinical pregnancy rate, and early miscarriage rate.

Randomization: randomized envelope method is used in the study. Random sequence is firstly generated by an independent statistician, secondly the grouping is randomized according to

random number and put into an opaque sealed envelope by the independent personnel, at last the investigator divides the subjects in line with the sealed envelope.

Random ratio: 1:1

Grouping: the treatment group takes RECO-18 while the control group takes the multi-vitamins.

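### Section 7.2 applies an open-ended logistic model of at least seven terms to every binary outcome: unusable for early miscarriage if only about 3–6 events are expected, mildly distorted for ongoing pregnancy

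*Combined protocol and SAP*

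**What the plan says.** Section 5.1 sets the enrolment: "At first it is designed to include 80 infertile patients (40 cases in each group"), and adds that "then the sample size is calculated based on the preliminary study results". Section 5.5 allocates 1:1 and names ongoing pregnancy at 12 weeks as the primary outcome. Clinical pregnancy and early miscarriage are among the secondary outcomes.

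For the primary outcome, Section 7.2 first states that "the two-sample rate test is used to compare the ongoing pregnancy rate at 12 weeks' gestation", using Pearson's chi-squared or Fisher's exact test, with a 95% confidence interval on the full analysis set. It then adds a logistic regression in which "the adjusted factors included age, infertility length, BMI, AMH, AFC, ovulation stimulation protocol, etc". For the secondary outcomes it repeats the Pearson or Fisher comparison and adds that "qualitative indicators are analyzed by Logistic regression to evaluate the baseline effects. Adjusted factors refer to the analysis of primary indicators".

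The documents give no expected pregnancy or miscarriage rate, and no definition or denominator for early miscarriage. They set no limit on the number of covariates and no rule for sparse events or a model that fails to converge. They do not say whether the adjusted or the unadjusted result decides.

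**The concern.** Six named covariates plus treatment make at least seven slopes, and the closing *etc.* leaves the list open. Whether such a model can be fitted depends on the number of events, and Section 7.2 uses one list for outcomes whose event counts are likely to differ by several-fold. When events are very few, some combination of seven terms often separates women with the event from those without. The likelihood then has no maximum, and the software either reports failure or prints an arbitrary, extreme odds ratio. With a moderate number of events the model fits, but small-sample bias pushes the odds ratio away from 1 and the model-based standard error is somewhat too small.

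At stake are the adjusted odds ratios the trial will report. An extreme adjusted odds ratio for miscarriage, in either direction, could be read as a safety or efficacy signal when it is an artefact of the fit. The open list also allows covariates to be added once results are known.

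**Working it through.** **Inputs from the documents.** 80 women, 40 per arm (5.1); 1:1 allocation (5.5); significance at 0.05, sidedness not stated, taken as two-sided; six named covariates (7.2). Two stimulation protocols are described in 5.8.5, so that factor costs one term. The treatment term is not written in 7.2 but is implied by an adjusted comparison. The plan gives no figure of its own to reproduce on this point.

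**Assumed, because the documents are silent.** Ongoing pregnancy rate 30–50%; 30–40 clinical pregnancies; early loss in 10–15% of them; moderate correlations among covariates.

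**Events per term, ongoing pregnancy.** 80 × 0.30 = 24 and 80 × 0.50 = 40 events. 24 / 7 = 3.4 and 40 / 7 = 5.7.

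**Events per term, early miscarriage.** 30 × 0.10 = 3 and 40 × 0.15 = 6 events. 3 / 7 = 0.4 and 6 / 7 = 0.9, so fewer than one event per term.

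**Early miscarriage, simulated with seven terms and no true effect.** Separation was detected by linear programming. Datasets with no miscarriage are counted as having no solution; they are about 4% of datasets at 32 pregnancies and 10% loss, and fewer in the other rows.

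| Clinical pregnancies | Loss | Expected events | No finite solution, 7 terms | Same, treatment only |
|---|---|---|---|---|
| 32 | 10% | 3.2 | 58–59% | 31% |
| 40 | 10% | 4.0 | 41–43% | 22% |
| 32 | 15% | 4.8 | 32% | 15% |
| 40 | 15% | 6.0 | 17% | 8% |
| 40 | 20% | 8.0 | 6–7% | 2% |

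A separate simulation with other covariate correlations gave about 51%, 36%, 25% and 8% at 3.6, 4.3, 5.4 and 8 expected events. Rounded, the range for 30–40 pregnancies and 10–15% loss is 20–65%. By exact number of events among 36 pregnancies, the rate is 89% at 2, 58% at 3, 32% at 4, 13% at 5, 7% at 6 and 1% at 8.

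If the denominator were all 80 women, the rate would be 27–52% at 4–5% miscarriage and 3–15% at 7.5–10%.

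A finite fit is not a safe one. In the 3–6 event range about 25–40% of finite fits had an odds ratio above 5 or below 0.2 although the true value was 1; at 8 expected events about a fifth still did.

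**Ongoing pregnancy, simulated with n = 80.** A finite solution was found in every run at 30–50%. Under no effect:

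| Event rate | Model | Mean SE / empirical SD | Wald type I error |
|---|---|---|---|
| 30% | 7 terms | 0.563 / 0.609 = 0.92 | 5.5% |
| 40% | 7 terms | 0.532 / 0.563 = 0.94 | 5.6% |
| 50% | 7 terms | 0.524 / 0.556 = 0.94 | 5.7% |
| 30–50% | Treatment, age, protocol | 0.97–0.98 | 4.6–5.0% |
| 30–50% | 7 terms, Firth | 1.03–1.04 | 3.4–3.8% |

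Across all the settings tried at n = 80, the standard error was about 3–9% too small and Wald type I error about 5–6%. With a true odds ratio of 2.0 (log 0.69), the mean estimated log odds ratio was 0.77–0.80, and exp(0.77) = 2.16 and exp(0.80) = 2.23. Against a model with treatment, age and AFC, the seven-term model has roughly 20–25% more variance for the treatment effect. That figure assumes AMH and AFC are strongly correlated and the other covariates nearly uninformative.

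**The case against.** The strongest reply is that the logistic models are secondary to simple comparisons. For the primary outcome, the unadjusted rate test and its interval come first and nothing here touches them. For early miscarriage, Fisher's exact test is already planned, so a failed regression still leaves a valid comparison. The protocol also calls itself a pilot study. All of this stands, and it limits the harm to the adjusted results. It does not remove the harm, because the plan still requires those results and never says which one decides.

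A reader might infer that the trial's primary conclusion rests on badly wrong standard errors. The documents do not support that: the first-listed test is unadjusted, and under plausible rates the adjusted model converges with Wald error near nominal. Likelihood-ratio error was a little higher in simulation (6.2–7.5%), but the documents name no likelihood-ratio test.

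A reader might also infer that the miscarriage model will fail often, whatever happens. That depends on an event count the documents do not give. At about four events or fewer, failure affects a third of datasets or more; at exactly 6 to 8 events it affects only 1–7%.

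Finally, which covariates to keep is partly a matter of preference. A three-term model is not the only remedy, since Firth's method handled all seven terms without a convergence failure. A short list of age and one reserve marker also gives up adjustment for stimulation protocol, which has two distinct forms in this trial.

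**Conclusion.** The point holds as a should-fix on the supplementary adjusted analyses. The text is clear: an open list of at least seven terms is applied to every binary outcome with no sparse-data rule.

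For early miscarriage the prescribed regression is unfit if about 3–6 events are expected. Between the fits that have no solution and those that are extreme by chance, most or a large share of datasets would yield nothing interpretable. The problem shrinks to about 8% without a finite solution at 8 expected events. Trimming covariates alone does not cure it, because treatment by itself still fails in 8–31% of datasets across 32–40 pregnancies and 10–15% loss.

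For ongoing pregnancy the effect on inference is mild; the more visible consequence is an odds ratio of 2.0 reported on average as about 2.2.

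These sizes rest on assumed event rates and covariate correlations, on a treatment term being in the model, and on the initial 80 women. A larger sample after the recalculation foreseen in 5.1 would ease them.

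**What to change.** In Section 7.2, before database lock and unblinding:

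1. Delete the adjusted logistic regression for early miscarriage. Report counts by arm with the already planned Fisher's exact test and an exact confidence interval, and state the denominator.
2. For ongoing and clinical pregnancy, delete *etc.* and fix a short closed list of baseline covariates, for example age and one of AFC or log AMH, not both. If the longer list is kept, fit it by Firth-penalised likelihood throughout and not only when a cell is empty.
3. State that the adjusted model supports the unadjusted rate comparison and does not replace it.

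The cost is a change of wording. With a short list, chance imbalance in BMI, infertility length or (if dropped) stimulation protocol is shown descriptively and not adjusted for. Firth's method is slightly conservative here (3.4–3.8% against 5%). The plan names only SPSS 19.0, so the sponsor should confirm that software for Firth's method is available.
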